4.1.1 Figure: Conceptual Model

4.2 Naltrexone (NTX) and Extended-Release Naltrexone (XR-NTX)

NTX is a potent opioid antagonist with high affinity for the mu-opioid receptor. In the U.S. it is approved for use in treating opioid dependence and alcohol dependence. It is highly efficacious in preventing relapse to opioid dependence provided that it is taken as prescribed, but adherence with oral naltrexone is problematic and leads to extremely high dropout rates, with the occasional exception of treatment in criminal justice and other settings where relapse may be linked to severe adverse consequences (Volpicelli, Rhines et al. 1997; O'Brien 2001; Rothenberg, Sullivan et al. 2002). This has led to intensive efforts - including NIDA- and NIAAA- funded grants to small businesses - to develop long-acting naltrexone preparations that can be administered as an injection or placed as an implant once per month or less frequently (NIDA 1976; Lobmaier, Kornor et al. 2008).

XR-NTX (Vivitrol[®], NTX-containing polylactide-co-glycolide [PLG] biodegradable sterile microspheres suspended in a diluent) is delivered by monthly injection into the muscles of the upper outer quadrant of the buttock. Each vial of microspheres contains 380 mg NTX which are suspended by adding a diluent that comes with the product and shaking for about a minute prior to injection of the full (less dead-space) content of the vial. Plasma concentrations of NTX and 6-beta naltrexol (its main active metabolite) after a single XR-NTX injection are detectable for at least 30 days. Consistent with this, in human laboratory studies with Vivitrol[®] and Depotrex[®], essentially complete blockade of opioid agonist effects is seen for 30 days (Comer, Collins et al. 2002; Bigelow, Preston et al. 2006). To maintain blockade beyond 30 days, XR-NTX must be re-administered. Long-term use of NTX and XR-NTX is not associated with tolerance, dependence, addiction or withdrawal on discontinuation. NTX and XR-NTX will, however, precipitate withdrawal in individuals physiologically dependent on opioids and decrease opioid tolerance.

As a consequence of its extended duration of action and assured treatment adherence, XR- NTX may dramatically and favorably alter the limited effectiveness profile associated with orally administered NTX. By ensuring 30-day medication adherence with a single injection, and thereby establishing a ~30 day mu-opioid antagonist blockade, the likelihood of an individual re- establishing opioid dependence during this period is very low. The two clinical trials cited above support efficacy for XR-NTX preparations compared to placebo injections (Comer, Sullivan et al. 2006; Krupitsky, Nunes et al. 2011).

The 2006 Comer et al. study (Comer, Sullivan et al. 2006) was a proof-of-concept, 2-month randomized, placebo-controlled trial with a subcutaneously administered product (Depotrex[®], Biotek Inc.), and showed that long-acting injectable naltrexone in conjunction with outpatient counseling produced superior treatment retention

to placebo, providing evidence of the feasibility, efficacy, and tolerability of long-lasting antagonist treatments for opioid dependence.

The Krupitsky et al. study (Krupitsky, Nunes et al. 2011) was conducted in 2008 and 2009 in 13 sites in Russia, and was sponsored by the manufacturer, Alkermes Inc. Following inpatient detoxification, 250 opioid-dependent participants were randomized to XR-NTX or placebo, double-blind monthly injections, for 6-months, during which all participants received outpatient counseling. The percent of opioid abstinent weeks, by weekly urine toxicology, was the primary outcome. A response profile analysis compared the cumulative percent of participants at each level of the outcome (percent opioid-free weeks) between the active XR-NTX and placebo conditions. The difference between the response profiles was significant ($p < .0002$), with the median participant on XR-NTX having 90% abstinent weeks compared to 35% abstinent weeks for the median participant on placebo. Total abstinence (100% opioid-free weeks) was reported in 45 (35.7%) participants in the XR-NTX group versus 28 (22.6%) participants in placebo group ($p < .03$). Retention in treatment for the full 6 months was 53% on XR-NTX, compared to 38% on placebo ($p < .02$). The 6-month retention rate in the 50% range is similar to that observed in clinical trials of buprenorphine (Mattick, Kimber et al. 2008). Participants treated with XR-NTX showed an approximately 50% sustained reduction in craving compared to no change in craving in the placebo group ($p < .005$). XR-NTX was generally well tolerated. Data from this trial supported Alkermes' supplemental NDA for treatment of opioid dependence.

Prescribing and Safety: Details on XR-NTX prescribing, pharmacokinetics and pharmacodynamics, metabolism and elimination, safety and toxicity are in the XR-NTX package insert.

4.3 Treatment as Usual (TAU)

The current standard of care for treatment of opioid use disorders in HIV clinics is opioid agonist therapy. Recent HIV treatment guidelines recommend office-based BUP/NX or referral for methadone maintenance for HIV-infected patients with opioid use disorders (Thompson, Aberg et al. 2012; Thompson, Mugavero et al. 2012). Through the efforts of the Health Resources and Service Administration (HRSA)-funded Buprenorphine and HIV Evaluation Study (BHIVES) and Substance Abuse and Mental Health Services Administration (SAMHSA)-funded Physician Support Service for Buprenorphine, on-site treatment with office-based buprenorphine is increasingly being offered in HIV clinics. A recent HRSA HIV/AIDS Bureau monogram promotes adoption of office-based buprenorphine in HIV primary care (HIV/AIDS Bureau Special Projects of National Significance Program 2012), see Section 4.1 for evidence of effectiveness of methadone and buprenorphine. Office-based BUP/NX, together with referral for methadone maintenance therapy, is now the standard of care for treatment of opioid use disorders in many U.S. HIV clinics (Thompson, Mugavero et al. 2012).

HIV-infected patients with alcohol use disorders are typically referred for residential, outpatient, and self-help groups (Burnam, Bing et al. 2001; Kraemer, McGinnis et al. 2006). Medication-assisted treatment of alcohol use disorders in HIV clinics is rare.

Many HIV clinics in the U.S., including all those associated with NIDA CTN nodes, receive Ryan White Care Act funding to provide ancillary services for under-insured and uninsured PLWHA. These services typically include on-site case managers, social workers, and substance use counselors who provide critical treatment, referral, and support services for HIV-infected patients with substance use disorders. The site selection process will include a thorough survey of existing treatment services.

4.4 Significance to the Field

Expanding HIV providers' armamentarium for treating alcohol and opioid use disorders and improving viral suppression in HIV-infected patients advances all three major goals of the National HIV/AIDS Strategy, including 1) Reducing new HIV infections, 2) increasing access to care and improving health outcomes for people living with HIV, and 3) reducing HIV-related disparities and health inequalities (The White House Office of National AIDS Policy 2010). The primary driver of HIV transmission is HIV viral load. If XR-NTX is effective in increasing viral suppression, fewer new HIV infections will occur among the sexual and drug using partners of opioid and alcohol dependent individuals (Wood, Kerr et al. 2009; Montaner, Lima et al. 2010; Cohen, Chen et al. 2011). The CHOICES study increases access to care by engaging HIV- infected participants with suboptimal viral suppression to initiate and adhere to ART, and improves health outcomes by increasing viral suppression with resultant improvements in health outcomes and decreased mortality. The CHOICES study reduces HIV-related disparities and health inequalities by seeking to engage opioid- and alcohol-dependent participants in HIV treatment—a vulnerable population with persistently suboptimal access to high quality HIV care and outcomes, compared with other HIV risk behavior groups. The CHOICES study also advances the science of opioid and alcohol use disorders treatment by directly comparing antagonist therapy with TAU in a non-inferiority comparative effectiveness trial to assess the implementation of a novel therapy into HIV clinical practice.

5.0 OBJECTIVES

5.1 Primary Objectives

The overarching goal of the CHOICES pilot study is to determine the acceptability and feasibility of XR-NTX in HIV practice and inform development of a multi-site comparative effectiveness trial of XR-NTX vs. TAU in HIV clinics. We will achieve this goal by pursuing four primary pilot study objectives. Specific measures of study objectives outcomes are defined in Section 8.0.

- Objective #1:** Assess HIV provider acceptability of antagonist therapy by estimating the proportion of HIV providers willing to prescribe XR-NTX for opioid and/or alcohol use disorders.
- Objective #2:** Assess HIV-infected patient acceptability of antagonist therapy by estimating the proportion of potential subjects approached willing to take XR-NTX and be randomized to a trial of XR-NTX vs. TAU.
- Objective #3:** Estimate the rate of participant recruitment into a future comparative effectiveness trial based on this pilot study.
- Objective #4A:** Compare successful treatment initiation within 4 weeks of randomization in participants randomized to receive XR-NTX vs. TAU for opioid and alcohol use disorders in HIV clinics.
- Objective #4B:** Compare treatment retention at 16 weeks following treatment initiation in participants randomized to receive XR-NTX vs. TAU for opioid and alcohol use disorders in HIV clinics.

5.2 Secondary Objectives

Secondary objectives are to generate point estimates for comparing the effectiveness of XR-NTX vs. TAU in:

- 1) HIV outcomes, as measured by:
 - a) HIV-1 RNA viral suppression (plasma HIV viral load of ≤ 200 copies/mL) at 16 weeks compared with screening.
 - b) Change in CD4 count at the week 16 visit compared with screening.
- 2) Change in Substance Use:
 - a) Change in 30 day opioid abstinence (by Addiction Severity Index (ASI)-lite self-report, Timeline Follow Back (TLFB) and urine drug screen (UDS) confirmation) in the final 30 days of the 16 week trial compared to screening.
 - b) Change in past 30-day alcohol and other drug use by ASI-lite, TLFB, and UDS at week 16 week visit, compared to screening.

3) Engagement in HIV Care, as measured by:

- a)** Change in the proportion of participants prescribed ART within 16 weeks following randomization compared to baseline.
- b)** Proportion of participants taking 100% of prescribed ART doses in the past 3 days at 16 weeks for those prescribed ART at any point during the 16 week trial.
- c)** Number of HIV primary care visits at 16 weeks. Adherence to HIV clinic visits in the year after ART initiation predicts HIV disease progression and death (Park, Choe et al. 2007).

4) Participant safety, as measured by:

- a)** Change in liver enzymes between screening and week 16 visit.
- b)** Any fatal and non-fatal opioid overdose between screening and week 16 visit
- c)** Change in Concise Health Risk Tracking between screening and week 16 visit.
- d)** Proportion of participants assigned to XR-NTX who develop precipitated opioid withdrawal.

6.0 STUDY DESIGN

6.1 Overview of Protocol Study Design

The CHOICES (CTN-0055) pilot study is designed to determine the acceptability and feasibility of XR-NTX in HIV clinical practice settings and to inform development of a multi-site comparative effectiveness trial of XR-NTX vs. TAU in HIV clinics. To maximize efficiency of research funding, we will begin data collection regarding feasibility during the study start-up period.

During the study start-up period (4-6 months duration), we will conduct a survey of HIV provider knowledge and attitudes about opioid antagonist therapy and other medication-assisted treatment at 15 high-volume HIV clinics as part of the study site selection process (Aim 1). Site selection will also survey clinic medical directors regarding clinic characteristics (number patients; providers; proportion of patients who are alcohol dependent only, opioid dependent only, or both, etc.), including an assessment of existing addiction treatment services (treatment as usual) for patients with alcohol and opioid use disorders in their clinic. HIV clinics will serve as community treatment programs (CTPs) for CTN-0055. Two clinics will be selected for the pilot study. Eligible study sites will: a) provide HIV primary care, b) have a sufficient population of potential participants to achieve study enrollment goals, c) have providers willing to be trained in use of XR-NTX for management of alcohol or opioid use disorders, d) have prior experience in participating in research/clinical studies, e) have the capacity to prescribe ART to participants, regardless of CD4 count, and f) offer on-site addiction counseling services as part of usual care.

The pilot study consists of a two-arm, 16-week, open-label, randomized, pilot trial of XR-NTX vs. TAU for treatment of opioid and alcohol use disorders in HIV-infected patients. Study participants are individuals with HIV infection and alcohol and/or opioid use disorders and who have received patient-centered information about both antagonist and agonist treatment options for alcohol and opioid use disorders. During screening, eligible participants will be surveyed regarding their attitudes about opioid antagonist therapy for opioid and alcohol use disorders (Aim 2). We will track the rate of participant recruitment (i.e., no more than 50 participants over no more than 12 months) to estimate duration of study recruitment required for a multisite study (Aim 3). Eligible patients are randomized in a 1:1 ratio to receive XR-NTX vs. TAU (Aim 4). Participants with both alcohol and opioid use disorders will be categorized by their self-reported substance of choice. XR-NTX (provided as Vivitrol®) will be administered by HIV clinic providers as a monthly intramuscular injection. Study visits will occur every 4 weeks for collection of blood and urine samples, safety, and other assessments. Primary outcomes of treatment initiation within 4 weeks of randomization, and retention at 16 weeks (maximum of 4 XR-NTX injections) and analyzed by intent-to-treat will be assessed. Secondary outcomes assessed at 16 weeks include change in 1) HIV-1 RNA viral suppression, 2) illicit drug and alcohol use, 3) HIV care engagement (receipt of ART, HIV visit adherence, ART adherence), and safety (percent with precipitated withdrawal, overdose, transaminitis).

6.2 Duration of Study and Visit Schedule

The CHOICES pilot study will target enrolling no more than 50 participants over no more than

12 months at 2 HIV clinic sites. Each participant will be engaged in the overall study for approximately 17-24 weeks (Figure 9.2) as follows:

- Up to 4 weeks: Consent, screening, randomization.
- Up to 4 weeks: Detoxification and induction.

- 16 weeks: Active treatment with monthly study visits.

6.3 Justification of 16 weeks active treatment and timing of ART initiation

The main purpose of this pilot study is to assess feasibility for a multisite trial. We have, therefore, opted to limit the length of treatment and follow up to 16 weeks. A multisite trial with a primary outcome of viral suppression would require a much longer duration of treatment (e.g., 36 weeks) in order to allow sufficient time for initiating ART and achieving viral suppression. Sixteen weeks, however, should provide sufficient time to assess the primary outcome of initial retention on study drug, since the majority of those lost to follow up in previous trials of XR-NTX for opioid or alcohol dependence occurred during the first 16 weeks (Garbutt, Kranzler et al. 2005; Krupitsky, Nunes et al. 2011).

7.0 STUDY POPULATION

7.1 Inclusion Criteria

Participating individuals in the provider acceptability survey are HIV providers, defined as any physician, nurse practitioner, or physician assistant who serves as primary HIV provider for HIV- infected patients at least one half day per week.

Individuals participating in the pilot study must:

- 1) Meet DSM-5 criteria for moderate or severe opioid use disorder and/or alcohol use disorder.
- 2) Be willing to be randomized to antagonist-based therapy or TAU for treatment of opioid and/or alcohol use disorders.
- 3) Be HIV-infected as defined by history of positive HIV serology or HIV RNA pcr > 10,000 copies/mL).
- 4) Be willing to establish ongoing HIV care at CTP if not already receiving ongoing care.
- 5) Be willing to initiate ART if not already prescribed ART, regardless of CD4 count.
- 6) Be at least 18 years old.
- 7) Be able to provide written informed consent and HIPAA (if applicable) for medical record abstraction.
- 8) Be able to communicate in English.
- 9) If female, be willing to take measures to avoid becoming pregnant.

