12.6 Clinical Laboratory Tests

Trained staff will be responsible for collecting and processing biologic specimens. Local laboratories at participating pilot sites will be used to conduct laboratory tests. Laboratories must be accredited by the College of American Pathologists (CAP) or equivalent, and participate in the Clinical Laboratory Improvement Act of 1998 (CLIA) or equivalent evidence of laboratory certification. Laboratories will provide reference ranges and proof of laboratory certification.

HIV-1 RNA PCR: will be drawn following randomization, and at 4, 8, 12, and 16 week follow-up visits (or end-of-medication/end-of-treatment if medication or TAU intervention stopped early) for outcomes assessment.

CD4 Count (T-helper cells): will be drawn following randomization and at 4, 8, 12, and 16 week visits (or end-of-medication/end-of-treatment if medication or TAU intervention stopped early) for secondary outcomes assessment.

Peripheral Blood Mononuclear Cells (PBMCs): For all participants, we will collect 4 CPT tubes for PBMC analysis following randomization and at the Week 4 visit or the first blood draw following study drug initiation. PBMC analysis will be conducted in a related NIH application to assess the effects of opioid blockade on TLR mediated immune responses. Samples must be drawn during CTN-0055 study implementation, but may be analyzed at a later time.

Safety labs: AST, ALT, CBC, INR, and urine pregnancy test (for females) will be performed to help determine eligibility at screening. Receipt and review of laboratory test results is necessary before confirming eligibility, conducting randomization and starting study medication. Results of laboratory tests conducted within 30 days prior to randomization (e.g., collected as part of routine detoxification admission) will be acceptable.

Liver profile: (AST, ALT, INR) will be repeated 1 week after study treatment initiation and at 4, 8, 12, and 16 week visits (or end-of-medication/end-of-treatment if medication or TAU intervention stopped early).

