17.3 Analysis of Randomized Pilot Study Primary Outcomes

The probability of treatment initiation (Aim 4A) and the probability of retention on treatment (Aim 4B), which are calculated separately for the two arms, are both based on ordinary (conditional) binomial samples, and will be estimated using maximum likelihood techniques, with exact binomial confidence intervals. We do not contemplate a multiplicity adjustment.

The rate of participant recruitment into the trial (Aim 3) can be estimated simply using maximum likelihood assuming an underlying Poisson process, but we feel it is more meaningful and useful for planning to predict the time required for recruitment in a subsequent randomized trial with 400 participants coming from 8 sites. We will do this via a bootstrap simulation. In each iteration of the simulation, the steps will be as follows:

- Draw a bootstrap sample of 8 sites from the 2 pilot-study sites.
- For each site, draw a bootstrap sample of, say, 1000 inter-arrival times from the inter-arrival times for that site to get 1000 simulated enrollment times (starting from time 0) for the site. Note that we consider that the time between the last enrollment at that site and the 12 month time point is also an inter-arrival time for that site. We will use this inter-arrival time in the simulation, but will not associate it with a simulated enrollment¹.
- Treating the 8 bootstrapped sites as simultaneously enrolling, determine T, the time of enrollment of the 400th patient in the simulated trial.

Repeating this iteration 10,000 times will generate 10,000 T-values that will constitute a predictive distribution for the enrollment times in the subsequent randomized trial. It is necessary to assume that the sites in the pilot study are a representative sample of the sites that will participate in the subsequent randomized trial.

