24.0 APPENDIX C

INFORMAL QUERY OF HIV CLINICS REGARDING PARTICIPANT AVAILABILITY FOR CTN-0055

To help inform protocol development, we conducted an informal query of HIV clinics affiliated with CTN nodes to inform CTN-0055 protocol development. This was not a site selection survey. HIV clinics not included in the informal query will still be considered for CTN 0055 participation. HIV clinic medical directors at these sites were e-mailed and asked to estimate: 1) the number of unduplicated HIV-infected potential participants per year at their site, 2) the number of opioid-dependent HIV-infected potential participants at their site, and 3) the number of HIV-infected potential participants with alcohol and opioid use disorders who had detectable HIV viral load. Thirteen of 17 HIV clinics responded.

Results in **Table 24.1** support the availability of more than 1,000 participants in 13 geographically diverse clinics. Eight of the responding HIV clinics are located in the “12 Cities Project”, cities that account for 44% of the U.S. AIDS cases and are targeted for expanded National HIV/AIDS Strategy HIV prevention and treatment activities by the U.S. Department of Health and Human Services (U.S. Department of Health and Human Services 2011). Three of the 13 respondents had fewer than 50 potential participants, though estimates for these sites were particularly conservative.

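### Enrollment is open at any viral load, while the feasibility count covers only unsuppressed patients and the week-16 suppression test ignores suppression status at entry

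*Protocol*

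**What the plan says.** **Eligibility.** Section 7.1 requires participants to "Be HIV-infected as defined by history of positive HIV serology", or alternatively by an HIV RNA result above 10,000 copies/mL. The RNA value is an alternative proof of infection, not a requirement to be viremic. No exclusion in section 7.2 concerns viral load. It could not be used to screen as scheduled, because section 12.6 says "HIV-1 RNA PCR: will be drawn following randomization, and at 4, 8, 12, and 16 week follow-up visits".

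**Feasibility.** Appendix C says the results in Table 24.1 "support the availability of more than 1,000 participants in 13 geographically diverse clinics", and adds: "Three of the 13 respondents had fewer than 50 potential participants". Section 7.7 relies on Appendix C for the clinic volume that a site needs.

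**Purpose.** Section 4.4 describes engaging HIV-infected "participants with suboptimal viral suppression to initiate and adhere to ART". Section 6.3 remarks: "A multisite trial with a primary outcome of viral suppression would require a much longer duration of treatment".

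**Analysis.** Sections 5.2, 8.2 and 17.2 define the suppression outcome at 16 weeks in comparison with screening. Section 17.5 fixes a chi-squared test of week-16 suppression against treatment assignment and names no baseline value. For ART prescription the same section does use baseline, scoring each person as follow-up minus baseline. For Aim 3, section 17.3 chooses "to predict the time required for recruitment in a subsequent randomized trial with 400 participants coming from 8 sites", by bootstrapping inter-arrival times of all randomized participants at the two pilot sites.

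**The concern.** The feasibility text counts one population and the eligibility criteria admit a wider one. The pilot's results pass to a larger trial for which section 6.3 discusses viral suppression as the primary outcome.

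Two outputs depend on who is suppressed at entry:

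- **The suppression estimate.** A participant unsuppressed at entry can gain suppression; one already suppressed can only keep or lose it. A single week-16 proportion per arm blends the two, and the blend depends on the case mix at two clinics. It cannot be carried to a trial with another case mix unless the parts are shown.
- **The recruitment forecast.** If the later trial admitted only unsuppressed patients, arrivals of suppressed participants in the pilot would not count toward its 400.

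**Working it through.** **1. Which column does the Appendix C text describe?** Sums and counts from the 13 clinics in Table 24.1:

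| Column | Total | Clinics below 50 |
|---|---|---|
| Opioid-dependent | 2,578 | 1 (47) |
| Lacking viral suppression | 1,159 | 3 (15, 20, 41) |

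The text gives more than 1,000 participants and three clinics below 50. Only the second column reproduces both.

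**2. Unsuppressed share, f.** Pooled: f = 1,159/2,578 = 0.450, so 0.550 would be suppressed. By clinic, f runs from 41/206 = 0.199 to 73/82 = 0.890, with median 0.50.

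**3. What the overall suppression difference contains.** Let d_u and d_s be the arm differences among participants unsuppressed and suppressed at entry. Then

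D = f × d_u + (1 − f) × d_s.

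The documents give neither d_u nor d_s. With an assumed d_u of 20 points:

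- d_s = 0: D = 0.45 × 20 = 9.0 points at the pooled share. Over the clinic range it is 0.199 × 20 = 4.0 to 0.890 × 20 = 17.8 points.
- d_s = 5: D = 9.0 + 0.55 × 5 = 11.7 points, which is 59% of d_u.
- d_s = 10: D = 9.0 + 0.55 × 10 = 14.5 points, which is 72% of d_u.

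Randomization is by site (section 9.2.8), with no stratification by viral load. With 25 per arm and f = 0.45, the chance difference between arms in the unsuppressed share has standard error √(2 × 0.45 × 0.55/25) = 0.14. Without a baseline term, such an imbalance passes into D.

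**4. The recruitment forecast.** The plan's figure first. At 2.28 per site-month, mean T = 400/(8 × 2.28) = 21.9 months. Treating T as gamma with shape 400, its 80th percentile is 22.8 months (Table 17.2.1 gives 23). At 1.14 the 80th percentile is 45.7 (table: 46). Both reproduce.

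If only a share f of arrivals qualifies, T becomes T/f:

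- f = 0.450: factor 2.2
- f = 0.890: factor 1.1
- f = 0.199: factor 5.0

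The factor does not depend on the recruitment rate. Applied to 2.28 as an illustration, the mean goes from 21.9 to 48.8 months at f = 0.450.

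**5. Size of the unsuppressed stratum.** 50 × 0.45 = 22, about 11 per arm. With assumed proportions of 30% and 50%, the 95% half-width for the difference is 1.96 × √(0.3 × 0.7/11 + 0.5 × 0.5/11) = 0.40, or about ±40 points.

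**The case against.** **The multisite trial's entry criteria are not given.** A reader might infer from sections 4.4 and 6.3 and Appendix C that it will take only unsuppressed patients. The protocol does not say so. Section 6.3 names an endpoint, not an entry restriction. Section 7.7 describes sites by patients with untreated opioid or alcohol use disorders, and section 17 gives only 400 participants from 8 sites. If that trial takes all comers, the section 17.3 forecast is on the right population. This stands, so the forecast point is conditional.

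**The 45% is weak.** It comes from e-mailed estimates, several of them a flat half. Appendix C describes the third query item as patients with alcohol and opioid use disorders and detectable virus, while the second item is opioid-dependent patients, so the columns may not share a base. Detectable is not the 200 copies/mL cut-off. Patients with alcohol use disorder alone are eligible, and recent methadone or buprenorphine maintenance is excluded. This stands: 55% suppressed is not a prediction for the pilot.

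**The effect need not be halved.** A reader might infer that suppressed entrants contribute nothing. They can rebound, and at different rates by arm; step 3 shows how much that changes. This stands.

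**48.8 months is not a forecast.** The 2.28 is a planning rate assumed for pilot and multisite trial alike, and the section 17.3 bootstrap uses observed arrivals instead. This stands; only the ratio 1/f carries over.

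**Subgroup reporting belongs in an analysis plan, and the outcome is secondary and hypothesis-generating.** This stands only in part. The protocol itself fixes a test without baseline for an outcome that it defines three times against screening. That is a mismatch within the document, not a detail left for later.

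**Conclusion.** The point holds in a limited form. From the document alone: enrollment is open at any viral load, the Appendix C count describes patients lacking suppression, and the section 17.5 test leaves out the baseline that sections 5.2, 8.2 and 17.2 put into the outcome. The all-randomized comparison is still valid as an arm comparison. What it lacks is a separation of gaining from keeping suppression, which the next trial's planners will need.

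The size is uncertain. On Table 24.1 the unsuppressed share is about 45% pooled and 20% to 89% by clinic; with two sites, anything in that range is plausible. The recruitment consequence arises only if the multisite trial excludes suppressed patients. The forecast would then be too short, with the time needed about 2.2 times the forecast at 45% and 1.1 to 5.0 times over the clinic range.

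For the pilot's own recruitment, the mismatch does not overstate the pool: within the opioid-dependent patients tabulated, eligibility is wider than the count.

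**What to change.** Leave eligibility as it is.

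1. **Section 17.5.** Keep the comparison of all randomized participants as the main suppression estimate, but stratify or adjust it for suppression status at entry. Define entry status by the viral load drawn at randomization, since the assessment table in section 10.1 schedules none at screening. Show the arm difference separately for participants unsuppressed and suppressed at entry.
2. **Section 17.3.** Run the bootstrap twice: on all randomized participants, and on those unsuppressed at entry, using the inter-arrival times between unsuppressed entrants at each site and the same handling of the final waiting time. This serves the multisite trial under either entry rule.
3. **Appendix C.** State that the count refers to patients lacking viral suppression.

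The cost is a few lines of text and a second run of the simulation, with no new visit or assay. The drawback is precision: with about 22 unsuppressed participants at 45%, the stratum estimates are descriptive only and should not replace the all-randomized figure as the one carried forward.
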